Therapist training. Therapists for MT will be post-doctoral level clinical psychologists or other licensed healthcare providers (e.g., nurse practitioner) with prior experience delivering MT for chronic pain. Therapists for SMT will be licensed PTs. Therapists at Rush and Vanderbilt sites will receive training prior to conducting treatment sessions with study subjects. Initial training will consist of a 2-day didactic and experiential course conducted by [name] and [name] for MT and [name] for SMT. Therapists will be provided detailed manuals and outlines of treatment protocols, and the treatment strategies will be taught via direct instruction, recorded illustrations of techniques, and role-play of common scenarios. All instruction sessions will be digitally videotaped for reference and/or education of new therapists. Therapists will be certified to deliver each treatment by having supervisors (i.e., Drs. [name], [name] and [name]) rate tapes of practice role-play sessions prior to their working with study subjects. Mastery of each protocol will be required for therapists to deliver treatment in the research protocol.

Procedures to ensure consistency of treatment. To ensure that the therapists consistently follow the appropriate treatment protocol, four steps will be taken: (a) use of a detailed treatment manual; (b) weekly supervision sessions; (c) audio or video recording of sessions for treatment adherence ratings (see below), with these recordings and feedback from the adherence raters reviewed during the weekly supervision meetings conducted by [name], [name] and [name]; and (d) provision

of therapist feedback on treatment consistency and further didactics and role plays to correct “drift” if needed.

Treatment adherence, and therapist competence. Adherence refers to the extent to which a therapist uses interventions prescribed by a protocol. Ratings of adherence to the treatments will be conducted by [name], [name], [name] and an RA. Protocol adherence criteria will be developed for each session with satisfactory adherence defined as 90% or more of the maximum possible score on the adherence rating scale. Ratings of therapists' competence in delivering the interventions will be used to evaluate 20% of the sessions for each of the treatment conditions. Sessions to be evaluated will be randomly selected.

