5.2 Handling of Study Interventions

This is not a study about drug efficacy. However, we will administer naloxone during half of the pain induction sessions in order to determine endogenous opioid (EO) function. We will use a placebo-controlled opioid blockade procedure to assess treatment-induced changes in EO function, by comparing pain responses under placebo to pain responses after opioid blockade with naloxone at pre- and post-treatment. Naloxone is an opioid antagonist with a brief half-life (1.1 hours; 78). We will use a weight-adjusted dose of 0.11 mg/kg with a maximum dose of 8mg (8mg dose for a 160 lb. individual, consistent with our past work 69-71). As in our past studies, naloxone in 20 ml normal saline will be infused over a 10-minute period through an intravenous cannula placed in the non-dominant arm. At this dosage, naloxone provides effective blockade of all three major opioid receptor subtypes (79). Naloxone is FDA approved, and appears to have no clinical effects in non-opiate dependent individuals. It has been used safely at similar dosages in previous studies, including our studies in CLBP samples (68-72). Peak naloxone activity will be achieved approximately 10 minutes following completion of the infusion. A second dose of naloxone (0.055 mg/kg with a maximum dose of 4mg; 4mg for a 160 lb. individual) will be infused following the thermal and ischemic tasks (before CPM procedures). This dose will be used to maintain adequate opioid blockade across the duration of pain-induction procedures.

MT and SMT treatments will consist of 8 weekly, 1-1.5 hr individual sessions delivered by a therapist. For MT and SMT, the content of each session will be based on a standardized treatment manual. Manuals will contain detailed session by session information, instructions and scripts for therapists, and patient handouts.

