9.2 Sample Size and Randomization

Power consideration for Aim 1:

Based on past findings, we expect that Mindfulness Training (MT) and Spinal Manipulation Therapy (SMT) will have near-equivalent effects on the primary outcome, changes in EO function. We ran power calculations assuming a true difference of 0 between MT and SMT. Please note that we plan to enroll 286 participants to achieve a sample size of 240 completed participants. See below:

Power Analysis of Two-Sample T-Test for Testing Equivalence Using Differences

Power	MT	SMT	Lower	Upper	True Difference	Standard Deviation	Alpha	Beta
	Group	Group						
	Sample Size (N1)	Sample Size (N2)	Lower	Upper	True Difference	Standard Deviation	Alpha	Beta
0.851	120	120	-3.0	3.0	0.0	7.5	0.050	0.149
0.950	120	120	-3.5	3.5	0.0	7.5	0.050	0.050
0.987	120	120	-4.0	4.0	0.0	7.5	0.050	0.013

An equivalence test of means using two one-sided tests on data from a parallel-group design with sample sizes of 120 in the reference group and 120 in the treatment group achieves 85% power at a 5% significance level when the true difference between the means is 0.0, the standard deviation is 7.5, and the equivalence limits are -3.0 and 3.

Power considerations for Aim 2:

We will test effects of MT and SMT on the treatment-specific mechanisms, pre-post treatment changes in mindfulness and spinal stiffness. Per reviewer suggestions and input from our co-I, [name], we expanded the assessment of “mindfulness” to include pain unpleasantness/bothersome ratings and the Multidimensional Assessment of Interoceptive Awareness (MAIA) scale as well as the Five Facets of Mindfulness Questionnaire (FFMQ). We expect MT to produce larger changes in the mindfulness measures than SMT, and for SMT to produce larger changes in spinal stiffness than MT.

Null Hypothesis: Mean1=Mean2. Alternative Hypothesis: Mean1 \neq Mean2

Allocation

Power	N1	N2	Ratio	Alpha	Beta	Mean1	Mean2	S1	S2
0.800	120	120	1.0	0.050	0.200	0.36	0.00	1.00	1.00
0.983	120	120	1.0	0.050	0.017	0.53	0.00	1.00	1.00

Treatment group sample sizes of 120 and 120 will achieve 80% power to detect a difference of Cohen's $d = 0.36$. With a larger effect – $d = .53$ -- at $\alpha=0.05$ we will have 98.3% power to detect a treatment difference.

Power considerations for Aim 3:

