9.6 Data Analyses

Primary analyses will be conducted on an ITT basis.

Aim 1: To determine the degree to which MT and SMT produce effects in nonspecific mechanisms.

The primary analyses will employ the two-sample t-test to compare mean change in each nonspecific mechanism within a noninferiority test construct to compare mean change in outcome from pre to post treatment between the two treatment arms. An overall, 2-sided, significance level of 0.05 will be used. Linear mixed models will be used as a supplemental analysis, allowing us to utilize all data collected, account for within subject variation, and model changes over time. The fixed effect part of the model will be

$Mechanism_{ij} = \beta_0 + \beta_1 Time_{ij} + \beta_2 Tx_i + \beta_3 (Tx_i * Time_{ij}) + \varepsilon_{ij}$ for subject i at visit j.

If β_3 is significantly negative ($p < .05$), this would indicate that the mechanism variable decreased more in SMT than in MT (Fitzmaurice, Laird, & Ware, 2011). In case of a significant interaction, we will test simple slopes of Time for each Treatment Condition separately AND by testing post treatment differences between MT and SMT controlling for pre-treatment values.

Candidate covariance structures will be assessed using the data's correlation structure and Akaike's Information Criterion (AIC). Random coefficients (e.g. random intercept and/or random slope) will be included in the model if they significantly improve the model fit as determined by the likelihood ratio test. Standardized residuals and Cook's distance will be used to assess the influence of outliers and individual observations. Residual plots will be used to check the multivariate normal distribution assumption. The pattern of missing data will be examined to determine its missing mechanism and the amount. If data are missing not at random (MNAR), data imputations may be used. If other deviations from the model assumptions are detected, appropriate measures will be taken to prevent inferential bias, e.g. data transformations and use of bootstrap techniques to compute standard errors.

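### Each arm has its own therapists, but Aim 1 power and the Aim 1 and 2 tests treat participants as independent; any positive therapist ICC raises false equivalence above nominal

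*Protocol*

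**What the plan says.** Section 5.1 assigns the two treatments to different professions: "Therapists for MT will be post-doctoral level clinical psychologists or other licensed healthcare providers", and for the other arm "Therapists for SMT will be licensed PTs". Section 5.2 describes one-to-one delivery: "MT and SMT treatments will consist of 8 weekly, 1-1.5 hr individual sessions delivered by a therapist". Nothing suggests that anyone delivers both treatments.

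Section 9.2 bases Aim 1 power on a TOST (two one-sided tests) calculation for 120 completers per arm and a margin of 3 units either way. The stated result is that it "achieves 85% power at a 5% significance level when the true difference between the means is 0.0, the standard deviation is 7.5". Section 9.6 then fixes the main analysis: "The primary analyses will employ the two-sample t-test to compare mean change in each nonspecific mechanism within a noninferiority test construct". Aim 2 also uses a two-sample t-test on change. The supplemental mixed models for both aims carry subject-level random effects only. The candidate covariates are site, age and baseline variables that differ between arms. Therapist does not appear, and the protocol gives no therapist number, caseload, ICC or design effect.

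**The concern.** Participants who share a therapist may have correlated outcomes. Because therapist is nested in arm, that correlation does not cancel in the arm comparison; it adds variance to it. A two-sample t-test leaves that variance out.

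The direction matters here because Aim 1 expects the arms to be near equivalent. A standard error that is too small makes it easier to place the interval inside the limits, so the error works in favour of the hypothesis. In Aim 2, a superiority comparison, the same omission raises the ordinary type I error. The protocol names both the test and the power basis, so this is a stated method and not simply a detail left for the analysis plan.

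**Working it through.** **Inputs from the protocol (9.2).** 120 per arm, SD 7.5, limits ±3.0, true difference 0, alpha 0.05, stated power 0.851 (0.950 at ±3.5 and 0.987 at ±4.0).

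**Assumed, because the protocol does not give them.** k = 3, 4, 6 or 8 therapists per arm; equal caseloads m = 120/k; one therapist per participant throughout; ICC = 0.01, 0.02 or 0.05; therapists regarded as a sample from a wider population.

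**Step 1, the plan's own figure.** With independent participants, SE = 7.5 × √(2/120) = 0.968. Exact TOST power with 238 df and 5% per side is 0.851, 0.950 and 0.987 at the three margins, matching the table. With 2.5% per side, power at ±3.0 would be 0.740, so the table uses 5% per side and no design effect.

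**Step 2, clustering.** Design effect DE = 1 + (m − 1) × ICC, and the true SE is 0.968 × √DE.
- False equivalence: probability that the unadjusted TOST passes when the true difference is 3.0.
- Adjusted power, normal approximation with DE known: 2Φ(3/SE − 1.645) − 1.
- Adjusted power with few clusters: the same calculation using t on 2k − 2 df.

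Example with k = 4 and ICC 0.05: m = 30, DE = 1 + 29 × 0.05 = 2.45, SE = 0.968 × √2.45 = 1.516. Normal-approximation power is 2Φ(3/1.516 − 1.645) − 1 = 0.26. The 90% interval half-width should be 1.645 × 1.516 = 2.49; the unadjusted analysis gives 1.645 × 0.968 = 1.59.

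| Therapists per arm | ICC | DE | False equivalence | Power, normal | Power, t on 2k − 2 df |
|---|---|---|---|---|---|
| any | 0 | 1.00 | 5.0% | 0.85 | not needed |
| 3 | 0.01 | 1.39 | 8.1% | 0.67 | 0.46 |
| 3 | 0.02 | 1.78 | 10.8% | 0.50 | 0.33 |
| 3 | 0.05 | 2.95 | 16% | 0.13 | 0.14 |
| 4 | 0.01 | 1.29 | 7.4% | 0.72 | 0.57 |
| 4 | 0.02 | 1.58 | 9.5% | 0.59 | 0.44 |
| 4 | 0.05 | 2.45 | 14.4% | 0.26 | 0.21 |
| 6 | 0.01 | 1.19 | 6.6% | 0.77 | 0.68 |
| 6 | 0.02 | 1.38 | 8.1% | 0.68 | 0.58 |
| 6 | 0.05 | 1.95 | 11.9% | 0.43 | 0.35 |
| 8 | 0.01 | 1.14 | 6.2% | 0.79 | 0.73 |
| 8 | 0.02 | 1.28 | 7.3% | 0.73 | 0.66 |
| 8 | 0.05 | 1.70 | 10.3% | 0.54 | 0.46 |

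A simulation of 20,000 trials per setting agreed: with 4 per arm, 7.3% at ICC 0.01 and 14.5% at 0.05; with 8 per arm, 6.0% and 10.2%.

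**Step 3, the other reading of alpha.** Section 9.6 gives an overall two-sided 0.05 for a noninferiority construct. If that means 2.5% per side, false equivalence over the same grid is 3.3 to 11.9% against a nominal 2.5%. It passes 5% only when DE exceeds (1.960/1.645)² = 1.42, which 6 of the 12 clustered cells do not reach.

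**Step 4, Aim 2.** The two-sided type I error is about 2Φ(−1.96/√DE). With 4 therapists per arm this is 8% at ICC 0.01 and 21% at ICC 0.05.

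**The case against.** A reader might infer that the Aim 1 test as planned has a false-equivalence rate above 5%. The protocol does not support that as a statement of fact. It needs a positive therapist ICC in the outcome tested, and at ICC 0 the rate is exactly 5.0% and the stated power is right. The 5% reference also comes from 9.2, whereas 9.6 can be read as 2.5% per side.

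There are good reasons to expect a small ICC for the primary mechanism outcome. Change in EO function is a pre-to-post change in a naloxone-placebo difference in evoked pain. It is measured in the laboratory by staff blind to arm (6.2.2, 6.2.3), and drug condition is double-blind. Delivery is tightly standardised through manuals, certification, weekly supervision, adherence ratings and, for spinal manipulation, a script (5.1). The study's interest in the therapeutic relationship does not show that naloxone effects differ between therapists, and the remark in 2.2 that it might explain a fifth of a treatment's effects is hypothetical.

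The cluster structure is inferred as well. The protocol does not say that one therapist keeps a participant for all eight sessions or that caseloads are equal, and its revision history records new physical therapists at one site. Finally, inference limited to these particular therapists would not carry the inflation.

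Most of this stands, and it argues for the low end of the range for EO function. It does not remove the point. The same test is applied to each non-specific mechanism, including working alliance and expectations, which depend far more directly on the individual therapist. The protocol also aims at conclusions about the two treatments as such. Even ICC 0.01 with 4 therapists per arm lowers power from 0.85 to 0.72.

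**Conclusion.** The point holds conditionally. The protocol assumes independence within therapist without giving the figures needed to judge that assumption. Any positive therapist ICC makes the standard error too small and lifts false equivalence above its nominal level, whichever reading of alpha applies. Over the assumed range and with 5% per side, the rate at the 3-unit margin is about 6 to 16%, and adjusted power (normal approximation) is about 0.79 down to 0.13. Allowing for few-cluster degrees of freedom lowers power further in all but the most extreme cell.

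The width of that range shows how little the document constrains the answer, so it is not an estimate of this trial's error rate. Nor do the figures justify replacing the primary test, since with so few therapists the variance component would be poorly estimated.

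**What to change.** 1. Record therapist ID for every session, and state the number of therapists per arm and site.
2. Keep the planned primary t-tests, but require a sensitivity analysis for Aims 1 and 2 with therapist, nested in arm, as a random effect and small-sample degrees of freedom. Qualify any equivalence conclusion that does not hold under it.
3. State in 9.2 that the 85% power assumes no therapist clustering, and show power over a range of ICCs and therapist numbers.
4. Reconcile the alpha in 9.2 (5% per one-sided test, equivalence) with 9.6 (two-sided 0.05, noninferiority).

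The cost is one recorded variable, one added analysis and revised wording, with no change to design or sample size. The downsides are a less favourable power statement and an imprecise therapist variance when therapists are few, so the sensitivity result must be read with that in mind.

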5.2 Handling of Study Interventions

This is not a study about drug efficacy. However, we will administer naloxone during half of the pain induction sessions in order to determine endogenous opioid (EO) function. We will use a placebo-controlled opioid blockade procedure to assess treatment-induced changes in EO function, by comparing pain responses under placebo to pain responses after opioid blockade with naloxone at pre- and post-treatment. Naloxone is an opioid antagonist with a brief half-life (1.1 hours; 78). We will use a weight-adjusted dose of 0.11 mg/kg with a maximum dose of 8mg (8mg dose for a 160 lb. individual, consistent with our past work 69-71). As in our past studies, naloxone in 20 ml normal saline will be infused over a 10-minute period through an intravenous cannula placed in the non-dominant arm. At this dosage, naloxone provides effective blockade of all three major opioid receptor subtypes (79). Naloxone is FDA approved, and appears to have no clinical effects in non-opiate dependent individuals. It has been used safely at similar dosages in previous studies, including our studies in CLBP samples (68-72). Peak naloxone activity will be achieved approximately 10 minutes following completion of the infusion. A second dose of naloxone (0.055 mg/kg with a maximum dose of 4mg; 4mg for a 160 lb. individual) will be infused following the thermal and ischemic tasks (before CPM procedures). This dose will be used to maintain adequate opioid blockade across the duration of pain-induction procedures.

MT and SMT treatments will consist of 8 weekly, 1-1.5 hr individual sessions delivered by a therapist. For MT and SMT, the content of each session will be based on a standardized treatment manual. Manuals will contain detailed session by session information, instructions and scripts for therapists, and patient handouts.

5.3 Concomitant Interventions

5.3.1 Allowed Interventions

Psychotropic medications and non-opioid analgesic medications are allowed.

5.3.2 Required Interventions

NA

5.3.3 Prohibited Interventions

Subjects taking daily opiates, even if not dependent, will be excluded from the study to avoid precipitating minor withdrawal symptoms.

Concomitant psychosocial treatments (e.g., cognitive behavioral therapy) and physical or manipulation therapies (e.g., PT, chiropractic) are prohibited for this study.

5.4 Adherence Assessment

The primary adherence index will be participant attendance of 6 out of the possible 8 sessions. A secondary adherence index for MT and SMT will be completion of inter-session homework assignments.

6. STUDY PROCEDURES

6.1 Schedule of Evaluations (see table)

Session	Pre-Treatment			Intervention								Post		Follow-up				
	Baseline	Lab 1	Lab 2	1	2	3	4			5	6	7	8	9		3m	6m	
Informed Consent	X																	
Demographics (SR)	X													Lab 1	Lab 2			
AEI (SR)															X			
Bothersome Pain Item (SR)	X			X*	X*	X*	X*			X*	X*	X*	X*			X	X	
Desirability of Control/Health Locus of Control (SR)																X		
Evoked Pain Intensity and Unpleasantness (SR)		X	X											X	X			
FFMQ-15/MAIA (SR)	X			X*	X*	X*	X*			X*	X*	X*	X*			X	X	
Healthcare Utilization (SR)	X														X	X	X	
Concomitant Medication	X	X	X											X	X	X	X	
HOME Opioid Questionnaire (SR)	X																	
McGill Pain Questionnaire (SR)		X	X											X	X			
MPQ (back pain- past week) (SR)	X													X		X	X	
Oswestry Low Back Disability (SR)	X													X		X	X	
Pain Catastrophizing Scale (SR)	X			X*	X*	X*	X*			X*	X*	X*	X*			X	X	
Pain Self-Efficacy Questionnaire (SR)	X			X*	X*	X*	X*			X*	X*	X*	X*			X	X	
PROMIS Anger/Anxiety/Depression/Pain Interference & Intensity/Sleep/Physical Function/Instrumental Support/Emotional Support (SR)		X			X*	X*	X*	X*			X*	X*	X*	X*			X	X
Working Alliance Inventory/Scale to Assess Therapeutic Relationship- Patient Version						X+					X+							
Reaction to Treatment Questionnaire (CEM)			X			X+					X+							
Pain Detect Questionnaire (SR)	X																	
Pain Stages of Change Questionnaire (SR)	X			X*	X*	X*	X*			X*	X*	X*	X*			X	X	
Naloxone Side Effects (SR)		X	X												X	X		
Patient Engagement Checklist (completed by therapist)				X	X	X	X			X	X	X	X					
Spinal Stiffness (before and after session- done via Vertetrack)				X	X	X	X			X	X	X	X					

Height & Weight (measured by scale)	X															
Blood Pressure (measured by Dinamap)	X															
Blood Draw (collected by RN)		X	X											X	X	
Urine Test (Opioid and Pregnancy-if female)		X	X											X	X	
Quantitative Sensory Testing		X	X											X	X	
If applicable: COVID-19 Safety Precautions (temperature check, travel history, signs/symptoms questionnaire)	X	X	X	X	X	X	X			X	X	X	X	X	X	X

*Survey is done via phone call with research assistant and research assistant enters directly into REDCap or survey is entered directly into REDCap online by participant

+ Survey is done via pen and paper by participant and entered into REDCap by RAs (therapist-blinded)

SR = self-report. Will be directly entered into REDCap by participant

6.2 Description of Evaluations

COVID-19 PRECAUTIONS FOR STUDY VISITS

Due to the COVID-19 pandemic (also known as the coronavirus), participants are asked to wear a face mask when they come attend study visits. No exceptions are allowed. Participants will have their temperature taken upon arrival and will be asked to self-screen for signs/symptoms of COVID-19 **before** coming to their visit. Upon arrival, staff may ask these questions again and if the participant is showing any signs/symptoms, they will be asked to reschedule their study visit. Study staff reserves the right to reschedule appointments if they think participants may be showing signs/symptoms of COVID-19. Study staff may add additional screenings for participants based on new recommendations and policies from RUMC, VUMC, Chicago Public Health Department, Metro Public Health Department, or other government agencies. During the COVID-19 pandemic, MT sessions may be conducted via Zoom with therapists and participants in separate rooms, but face-to-face on an iPad to protect the safety of therapists and participants.

6.2.1 Phone Screening Evaluation

Potential participants responding to ads, flyers, etc., will be contacted by phone after indicating their desire to be contacted (via e-mail or phone call). They will be asked whether they agree to provide basic medical information in order to determine their study eligibility. If responding positively, they will be asked whether they have daily pain of at least 3 months duration, which is of an average intensity of at least 4/10 (with 0 being “no pain” and 10 “the worst pain possible”), and presents substantial interference in performance of social, work, and everyday activities ($\geq 3/10$ on a 10-point scale). They will be asked whether: 1) their pain is musculoskeletal pain of the lower back and/or leg; 2) they are aged between 18 and 75 years; 3) can understand English well enough to complete questionnaires or to participate in therapy; 4) their pain is due to malignant conditions, rheumatoid arthritis, complex regional pain syndrome, or fibromyalgia syndrome; 5) they have had lumbar surgery within the past 6 months or have ever had spinal fusion surgery; 6) they are pregnant; 7) they have had liver disease such as hepatitis or cirrhosis; 8) they have osteoporosis; 9) they have any active suicidal ideation with intent; 10) they have opioid-dependency or use Kratom daily; 11) they can hold their breath for 15 seconds; 12) they have acute trauma to spine; 13) they have long term use of corticosteroids; 14) they have a spinal cord stimulator, IT pump, or a similar device; 15) they have signs of nerve root compression (i.e., positive straight-leg raise $<45^\circ$); 16) they meet criteria for past or present psychotic or bipolar disorders; 17) arthritis of the hand, carpal tunnel syndrome, or any neuropathic pain diagnoses affecting the upper limbs; and 18) they have a BMI of ≥ 40 . If they meet eligibility criteria, they will be invited to an in-person interview.

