4.1 Inclusion Criteria

Inclusion criteria are: 1) musculoskeletal pain of the lower back and/or leg pain stemming from degenerative disk disease, spinal stenosis, or disk herniation (radiculopathy subcategory), or muscular or ligamentous strain (chronic myofascial pain subcategory); 2) able to verify chronic pain diagnosis via written confirmation

from a physician; 3) significant daily chronic pain intensity (≥ 4 on a 10-point scale) and interference in performing daily activities due to pain (≥ 3 on a 10-point scale) for at least 3 months; 4) age 18-75 years, and 5) not using opioid analgesics or Kratom on a daily basis or within 3 days of each laboratory session (confirmed via urine drug screen).

Eligibility will be determined by MD review of medical records and RA administration of relevant items from the Mood Disorder, Psychotic Screening and Substance Use Disorders Modules of the Structured Clinical Interview for DSM-V Axis I Disorders - Non-Patient Edition (SCID-V/NP;77). General health will be assessed as will circumstances of the onset of low back pain, the sequence of events in terms of medical intervention to date, exacerbating/ameliorating factors, medications used currently and in the past, previous diagnostic modalities employed, and previous medical interventions and their impact.

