Interested individuals will be able to contact the designated study research assistant by phone or email. Individuals expressing an interest will first be provided verbally with information on the study procedures, risks, and benefits, and if interested, will be given the opportunity to read the IRB-approved informed consent form. All questions from potential subjects will be answered by the study representative as accurately as possible. All individuals agreeing to participate will provide written informed consent prior to beginning any study procedures. Subject recruitment and consent procedures will be carried out by individuals designated and trained by each site PI and the IRB to carry out these procedures (i.e., the proposed research assistants). Potential subjects will be told that they will be compensated \$605 for their time and effort to participate in all of the assessment and therapy sessions. In the Consent Form, it will be emphasized that subjects may discontinue participating at any time and still receive prorated compensation. The recruiter will inform potential subjects that participation is completely voluntary, and they may withdraw at any time without penalty or running the risk of jeopardizing current and future treatment at the Rush or Vanderbilt medical centers.

Study patients (n=286) will be randomized to receive either MT or SMT. The order of drug administration for each laboratory session will also be separately randomized and counterbalanced (placebo vs. naloxone) for both of the assessment time points (in double-blinded fashion). All randomization will be carried out using the Proc Plan procedure in SAS version 9.2 (SAS Institute, Cary, NC). This SAS procedure will be used to generate a randomization schedule for each sequential study slot (MT vs. SMT and the order of naloxone/placebo administration in each set of lab visits). Study subjects will be assigned to these previously randomized study slots in the order that they are enrolled, and the previously determined randomization status associated with each slot will determine the intervention condition each subject is in and the order of drug administration for each session. This randomized order will be maintained even if study appointments are missed (applies only to drug order in laboratory sessions). In the event of a true study dropout, that slot is considered used and future subjects will not be assigned to that slot.

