6.2.2 Consent, Detailed Screening, Enrollment, Baseline, and/or Randomization

Consenting Procedure

All individuals agreeing to participate will provide written informed consent during Visit 1 (i.e., prior to beginning any study procedures). Subject consent procedures will be carried out by individuals designated and trained by each site PI and the IRB to carry out these procedures (i.e., the proposed research assistants). In the Consent Form, it will be emphasized that subjects may discontinue participating at any time and still receive prorated compensation. The recruiter will inform potential subjects that participation is completely voluntary, and they may withdraw at any time without penalty or running the risk of jeopardizing current and future treatment at the Rush or Vanderbilt medical centers. Consent forms with identifiable subject information will be maintained in a separate locked file from the actual study data files, which will be identified only by subject number. All subjects will be informed regarding how HIPAA requirements may impact on their study records, and will sign a notification regarding this issue. All published data will be reported in a manner in which individual data for specific subjects are not identifiable.

Screening

Screening can occur from 1 month prior to study enrollment to the day before study enrollment.

Screening evaluations will consist of:

- demographics
- confirmation of diagnosis of chronic low back pain
- pain duration and intensity ratings
- medical history
- list of current medications, prescribed dose and reported actual dose taken
- list of over the counter medications
- psychological screening: SCID-IV/NP

Please see sections 4.1 and 4.2 for inclusion/exclusion criteria. The criteria will be examined once all screening assessments are complete so as to not alert participants to our precise screening criteria.

Enrollment

The enrollment date is day the individual has met all the screening criteria and signs the informed consent form.

Baseline Assessment (Visit 1)

- Pain interference (primary outcome), pain intensity, negative affect (anger, anxiety, depression), physical function, sleep disturbance and social support will

be assessed via designated Patient-Reported Outcomes Measurement Information System (PROMIS) forms for each construct.

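### Section 6.2.1 puts the exact pain and interference cut-offs to callers as threshold questions, which undercuts the concealment of criteria intended in section 6.2.2

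*Protocol*

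**What the plan says.** Section 4.1 sets these limits, both to hold for at least 3 months: "significant daily chronic pain intensity (≥ 4 on a 10-point scale) and interference in performing daily activities due to pain (≥ 3 on a 10-point".

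Section 6.2.1 describes the phone contact. Callers are "asked whether they have daily pain of at least 3 months duration, which is of an average intensity of at least 4/10", and whether the pain "presents substantial interference in performance of social, work, and everyday activities", with the limit of 3/10 stated. The call decides who goes further: "If they meet eligibility criteria, they will be invited to an in-person interview".

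Section 6.2.2 then describes detailed screening. Its list includes "pain duration and intensity ratings" but no interference rating. It closes with a safeguard: "The criteria will be examined once all screening assessments are complete so as to not alert participants to our precise screening criteria". The baseline assessment at Visit 1 follows, with PROMIS forms for pain interference (the primary clinical outcome), pain intensity and other domains.

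Section 4.3 states compensation of $605 "for their time and effort to participate in all of the assessment and therapy sessions", prorated for those who stop early.

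**The concern.** The sponsor chose to keep the criteria from participants. Asking a caller whether pain is at least 4/10 and interference at least 3/10 tells that caller which answers admit. A person just below a limit who wants to take part can then report a value at or above it, and knows the limits when the ratings are repeated.

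Two things are at stake. The first is the entry population, because people with true ratings below the cut-offs may be admitted. The second is the clinical baseline. Pain and interference are also outcome domains, and there is no untreated arm. If raised reporting reaches the Visit 1 measures and later reports are candid, part of the pre-post fall within each arm is not treatment response. The same excess enters the outcome change scores that Aim 3 sets out to predict.

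**Working it through.** The protocol gives no figure for misreporting at entry, so there is none to reproduce. The check compares the sections and then illustrates a size under stated assumptions.

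**1. The limits, section by section**

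| Criterion | 4.1 | Put to the caller in 6.2.1 | Detailed screening list in 6.2.2 |
|---|---|---|---|
| Pain intensity | ≥4/10 | ≥4/10 | rated again |
| Interference | ≥3/10 | ≥3/10 | not listed |
| Duration | at least 3 months | at least 3 months | rated again |

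All three limits in 6.2.1 equal those in 4.1. For interference, the phone question is the only step at which the protocol describes asking about the 0-10 criterion. No section says that the limits are withheld by phone or that open ratings are collected.

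**2. The order of events**

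The phone questions come first and act as a gate. Consent, the repeated ratings, the examination of criteria and the PROMIS baseline come later. Withholding the limits at the later stage cannot undo their disclosure at the earlier one.

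**3. Possible size (assumptions, not protocol figures)**

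False within-arm fall = share of entrants who raised their rating × average rise among them.

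Assumed for a simulation:
- True pain among callers is normal with mean 4.5 to 5.5 and SD 1.5 to 2.0, kept within 0-10, and callers with true pain below 2 are left out.
- Ratings are whole numbers.
- A fraction q of callers who would rate below 4 report 4.
- The raised rating carries over fully to baseline, later ratings are candid, and treatment has no effect.

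| Mean, SD | q | Share of entrants inflated | False fall (0-10 points) |
|---|---|---|---|
| 5.5, 1.5 | 25% | 2.2% | 0.025 |
| 5.5, 1.5 | 100% | 8.3% | 0.095 |
| 5.0, 1.5 | 50% | 7.4% | 0.087 |
| 4.5, 2.0 | 25% | 6.8% | 0.085 |
| 4.5, 2.0 | 100% | 22.6% | 0.285 |

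The first and last rows are the extremes of the 18 settings run with q above zero. In the last row the average rise is 0.285 / 0.226 = 1.26 points. With q = 0 the fall is 0.

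**4. What is and is not affected**

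Write the excess in the baseline report as u. Observed change (post minus baseline) is true change minus u.
- Within an arm, the mean change shifts by minus the mean of u.
- Between arms, the shift is the difference of the two arm means of u. This is zero in expectation if u arises before treatment and is unrelated to allocation. In the simulation it was at most 0.002 in absolute value, which is simulation error.
- In Aim 3, u adds variation to the pre-post outcome change that no mechanism explains.
- EO function comes from evoked pain under placebo and naloxone in the laboratory, not from the screened ratings.

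**The case against.** The best defence is that 6.2.1 is a prose summary and not the script, which is not in the protocol. Its list includes items that can hardly be read out to a caller, such as a straight-leg-raise sign or meeting criteria for a psychotic disorder, and it gives the anchors of the 0-10 scale, which fits collecting a rating. The safeguard in 6.2.2 can also be read as governing only the detailed screening. This stands as a reason for caution: disclosure is what the text describes, not something shown to have happened. If the script does ask for open ratings, 6.2.1 misdescribes it and still needs correcting.

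Other points stand and limit the consequence:
- The gates are 0-10 items, whereas the outcomes are PROMIS forms with no disclosed limit. Section 6.2.2 lists the PROMIS baseline after enrollment, by which time the reason to qualify may have passed. The order is not fully clear, because the same section calls Visit 1 the baseline screening visit.
- A reader might infer that all later concealment is useless. It is not: medical record review, physician confirmation of the diagnosis, psychiatric interview items and urine testing do not rest on the caller's rating.
- The payment is a modest motive. It is prorated over 15 visits (1 + 2 + 8 + 2 + 2), about $605 / 15 = $40 each.
- Entry thresholds without an untreated arm already leave within-arm change open to regression to the mean, however the question is worded.

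**Conclusion.** The conflict between 6.2.1 and 6.2.2 holds on the text: one section discloses limits that the other intends to keep from participants. The consequence is a risk, not a demonstrated error. Some people below the cut-offs may enter. If inflation carries over to the PROMIS baseline, within-arm improvement is somewhat overstated and the Aim 3 change scores carry extra noise.

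The size cannot be derived from the protocol. The range of about 0.03 to 0.29 points depends wholly on the assumed distributions, the assumed fraction q and full carry-over, and points on a 0-10 item do not convert directly to PROMIS scores.

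A reader might infer that the treatment comparison is biased. The documents do not support this, since the inflation precedes treatment and should be equal in both arms so long as candidates do not know their allocation when they give these ratings. Nor do they support a bias in the primary EO outcome. A reader might also infer that mechanism-outcome associations are biased in a definite way. Extra variation in the outcome change would mainly weaken them, and the lagged tests of Aim 4 predict mid-to-post change, which baseline enters only through the pre-to-mid terms.

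This is worth correcting because it restores the sponsor's own safeguard at almost no cost.

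**What to change.** Reword 6.2.1 and the phone script so that staff ask for average pain (0-10), interference with activities (0-10) and duration in months, without stating any limit. Staff apply the cut-offs afterwards, out of the caller's hearing, and then decide on the invitation. Align 6.2.1 with the safeguard in 6.2.2. No eligibility limit, visit or sample size changes.

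For people already screened, check the script that was used. If it disclosed the limits, say so when within-arm change is interpreted. If it did not, correct the description in 6.2.1 only.

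The cost is one edit to the script and one to the protocol text, with no added time or staff.
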